Appendix J Contraception Guidance

For females:

Females without childbearing potential will be included in this study. Females without childbearing potential are defined as those who are surgically sterile (ie, women who have had a hysterectomy, bilateral ovariectomy (oophorectomy), bilateral salpingectomy, or bilateral tubal ligation) or those who are postmenopausal (defined as 12 months or more with no menses without an alternative medical cause).

For males:

Nonsterilised males who are sexually active with a female partner of childbearing potential must use condom and spermicide for the duration of the treatment period and 3 months and 20 days after the last administration of investigational product (IP). As male condom and spermicide are not considered to constitute a highly effective contraception method, female partners of male study participants must also use a highly effective method of contraception for the duration of the treatment period and for 3 months and 20 days after the last administration of IP. A highly effective method of contraception is defined as one that results in a low failure rate (ie, less than 1% per year) when used consistently and correctly.

The acceptable methods of contraception are described in Table J13.

Table J13Highly Effective Methods of Contraception

Barrier Methods	Hormonal Methods		
Intrauterine device	Combined (oestrogen and progestogen containing hormonal contraception)		
Intrauterine hormone-releasing system (UIS) ^a	\forall Oral (combined pill)		
Bilateral tubal occlusion	∀ Injectable		
Vasectomised partner ^b	\forall Transdermal (patch)		
Sexual abstinence ^c	Progestogen-only hormonal contraception associated		
	with inhibition of ovulation ^d		
	∀ Injectable		
	\forall Implantable		
	\forall Intravaginal		

^a This is also considered a hormonal method.

^b With appropriate postvasectomy documentation of surgical success (absence of sperm in ejaculate).

^c Sexual abstinence is considered a highly effective method only if defined as refraining from heterosexual intercourse during 3 months and 20 days after the last IP administration and if it is the preferred and usual lifestyle of the participant.

^d Progestogen-only hormonal contraception, where inhibition of ovulation is not the primary mode of action (eg, minipill), is not accepted as a highly effective method).

IUS, intrauterine system

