- ^t A urine pregnancy test (applicable for women who are not surgically sterile) should be performed and the results assessed at all dosing visits prior to IP administration and at the Week 36 visit. The results must be negative in order to proceed with IP administration (Section 8.2.11.2).

CCI	
V	Abnormal haematology, chemistry, or coagulation tests could be repeated once for confirmation (Section 8.2.11).
CCI	
Z	Participants who develop unacceptable pain (including the washout period) will be permitted to initiate rescue therapy with paracetamol. Study sites will provide the rescue medication at the indicated visits. Rescue medication will be recorded daily from Day -14 until the FU visit at Week 18. Participants who discontinue IP early, will stop recording rescue medication after the ET visit (Section 6.5.3).
aa	Participants will bring the rescue medication (bottles/cartons/blisters) at each study visit to assess rescue medication compliance. Site staff should check returned paracetamol against what the participant has recorded in their diary. Participants will return all unused paracetamol at the Week 18 visit. Participants who discontinue IP early will return all unused paracetamol at the ET visit (Section 6.5.3).
bb	Participants who discontinue IP prematurely may be given standard-of-care therapy for their pain after the ET visit as deemed appropriate by the investigator (Section 7.1.2).
сс	The screening will be implemented until there is no perceived risk from COVID-19 for participants to take part in the study; COVID-19 symptom screening, body temperature check, and SARS-CoV-2 testing may also be conducted at other time points at the discretion of the investigator.
dd	The SARS-CoV-2 test will be implemented until there is no perceived risk from COVID-19 for participants to take part in the study; a test sample to be taken within 72 hours prior to each dosing visit (on Days 1, 14, 28, 42, 56, and 70) (Section 4.1.2).
	PM, ambulatory blood pressure monitoring; ADA, antidrug antibody; ACPA, anti-citrullinated protein antibodies; BMI, body mass index; COVID-19, coronavirus disease
	9; COX-2, cyclooxygenase-2; D or d, day(s); CCI ; DSIS, Daily Sleep Interference Scale; ECG, electrocardiogram;
	F, end of treatment; ePRO, electronic patient-reported; ET, early termination; FSH, follicle-stimulating hormone; CCI ; HIV, human

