5.1 Inclusion Criteria

Participants are eligible to be included in the study only if all of the following criteria apply:

General/Informed Consent

- 1 Participants must understand the nature of the study and must give signed and dated written informed consent prior to the initiation of any study procedures as described in Appendix B, which includes compliance with the requirements and restrictions listed in the informed consent form (ICF) and in this protocol.
- 2 For participants participating in the optional genetic research, a separate signed and dated optional genetic research ICF must be provided prior to collection of samples for optional genetic research that supports the Genomics Initiative. If a participant declines to participate in the genetic research, this will have no influence on the ability of a participant to participate in the study.
- 3 The participant should be willing and able to understand and comply with all protocolspecified restrictions and procedures and be able to use an electronic patient-reported outcome (ePRO) device as judged by the investigator.
- 4 The participant must be considered likely to comply with the study protocol and to have a high probability of completing the study, as judged by the investigator.
- 5 The participant must be willing and able to discontinue analgesic therapy for OA with NSAID or COX-2 inhibitors from the start of the washout period until the end of the FU period. This includes over-the-counter (OTC) pain medications and topical analgesics that contain an NSAID or COX-2 inhibitor. There are additional restrictions for medications use during the different periods of the clinical study; refer to Section 6.5 for permitted and prohibited medications.

Age/Gender/Weight

- 6 Study participants will be males or postmenopausal or surgically sterile females, 18 to 80 years of age (inclusive) on the day of randomisation.
 - # Surgically sterile women are defined as those who have had a hysterectomy, bilateral ovariectomy (oophorectomy), or bilateral tubal ligation. Women who are surgically sterile must provide documentation of the procedure by an operative report or by ultrasound.
 - # Postmenopausal women are defined as follows:
 - Women < 50 years old would be considered postmenopausal if they have been amenorrhoeic for 12 months or more following cessation of exogenous hormonal treatment and follicle stimulating hormone (FSH) levels are in the postmenopausal range.

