All participants must stop taking their current pain medication for at least 48 hours or 5 halflives, whichever is longer, prior to the start of the daily NRS pain score baseline period on Day -7. Half-lives of commonly used pain medications are shown in Appendix K. The list is not all-inclusive. The Physician's Desk Reference provides half-life information.

Double-blind Treatment Period

The following procedures will be performed on Day 1 prior to randomisation:

- \forall Inclusion and exclusion criteria confirmation
- ∀ Urine pregnancy test (for women who are not surgically sterile only; the results must be negative in order to proceed with IP administration)
- ∀ Urine samples for biomarkers (fasting) should be from the second morning void of the day or after. Refer to Section 8.6.1.4 for additional information.
- ∀ Daily pain diary (NRS)
- ∀ DSIS
- ∀ TNSn
- ∀ Physical and neurological examination
- ∀ Supine BP and pulse rate (prior to any blood draw)
- ∀ Orthostatic BP (after supine BP, 1 and 3 minutes after the participants stands and prior to any blood draw)
- ∀ Body temperature (prior to any blood draw)
- ∀ Respiratory rate (prior to any blood draw)
- ∀ ECG (30 to 120 minutes prior to IP administration and prior to any blood draw)
- ∀ Urinalysis

The following procedures will be performed on Day 1 after randomisation but prior to administration of IP:

- \forall WOMAC index
- ∀ PGA
- ∀ CCI
- ∀ Survey of Autonomic Symptoms (SAS)
- ∀ Blood collection for haematology, chemistry, coagulation, PK, ADA, PD, CCI

The following procedures will be performed on Day 1 after randomisation and administration of IP:

- \forall ECG will be performed 4 hours \pm 30 minutes after IP administration.
- ✓ Supine BP and pulse rate measurements will be performed at 5 ± 5 minutes after completion of IP administration, and 30 ± 5 minutes, 60 ± 10 minutes, 2 hours ± 10 minutes, and 4 hours ± 10 minutes after the start of IP administration.
- ∀ Body temperature measurements will be performed at 5 ± 5 minutes after completion of IP administration, and 30 ± 5 minutes, 60 ± 10 minutes, 2 hours ± 10 minutes, and 4 hours ± 10 minutes after the start of IP administration.
- \forall Respiratory rate measurements will be performed at 5 ± 5 minutes after completion of IP administration, and 30 ± 5 minutes, 60 ± 10 minutes, 2 hours ± 10 minutes, and 4 hours ± 10 minutes after the start of IP administration.

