8.2.11.2 Pregnancy

Serum pregnancy testing for β -human chorionic gonadotropin is applicable for female participants not surgically sterile and will be performed at screening as indicated in the SoA (Table 1). Urine pregnancy tests will be conducted at all dosing visits prior to IP administration as indicated in the SoA (Table 1).

Female participants who are not surgically sterile must not have a positive pregnancy test at screening as specified in inclusion criterion 6. A woman who is found to be pregnant at the screening visit will be excluded from the study and be considered a screen failure.

Urine pregnancy testing will be conducted prior to each IP administration on every woman who is not surgically sterile.

Women should be instructed to contact the investigator or study staff immediately if pregnancy occurs or is suspected.

Procedures to be implemented if a woman becomes pregnant during the study and pregnancy reporting requirements are found in Section 8.3.10.

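### A premenopausal woman admitted on bilateral tubal ligation alone is exempt from all 8 scheduled pregnancy tests, although Table J13 counts tubal occlusion in a partner as contraception

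*Protocol*

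**What the plan says.** Section 5.1, criterion 6, sets who may enrol: "Study participants will be males or postmenopausal or surgically sterile females, 18 to 80 years of age (inclusive) on the day of randomisation". It then defines the surgical route: "Surgically sterile women are defined as those who have had a hysterectomy, bilateral ovariectomy (oophorectomy), or bilateral tubal ligation". These women must document the procedure with an operative report or ultrasound. Appendix J places women without childbearing potential in the same two groups, and its surgical list is "women who have had a hysterectomy, bilateral ovariectomy (oophorectomy), bilateral salpingectomy, or bilateral tubal ligation".

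The testing rules all use the same label:

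- Section 1.3, Table 1 footnote t: "A urine pregnancy test (applicable for women who are not surgically sterile) should be performed and the results assessed at all dosing visits", and again at Week 36.
- Section 8, Day 1 list: "Urine pregnancy test (for women who are not surgically sterile only; the results must be negative in order to proceed with IP administration".
- Section 8.2.11.2: the serum test "is applicable for female participants not surgically sterile and will be performed at screening as indicated in the SoA".
- The criterion 6 note, the laboratory list in Section 8.2.11 and Section 8.3.10.1 carry the same restriction.

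In Appendix J, the part for male participants requires their female partners of childbearing potential to use a method from Table J13. One entry is "Bilateral tubal occlusion". The class is defined so: "A highly effective method of contraception is defined as one that results in a low failure rate (ie, less than 1% per year".

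**The concern.** Criterion 6 joins its two routes with an or. A premenopausal woman can qualify through tubal ligation alone, and the label that admits her also removes every scheduled pregnancy test. The women who are tested before each dose are those who qualify through menopause.

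The same appendix treats closure of the tubes in two ways. In a partner it is contraception with a low but non-zero permitted failure rate, and the male participant must still use condom and spermicide. In a participant who receives the product directly it is absence of childbearing potential, with no second method and no test.

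What is at stake is fetal safety. Section 8.3.10.1 bars women of childbearing potential and relies on testing before dosing. In this group, a pregnancy present at entry or arising during the six doses would come to light only if the woman suspected it or a clinician chose to test.

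**Working it through.** **Step 1: tests scheduled per woman** (Table 1 with footnote t; Sections 8, 8.2.11 and 8.2.11.2).

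| Woman admitted under criterion 6 | Serum, screening | Urine, 6 dosing visits | Urine, Week 36 | Total |
|---|---|---|---|---|
| Postmenopausal, not surgically sterile | 1 | 6 | 1 | 8 |
| Hysterectomy or bilateral oophorectomy | 0 | 0 | 0 | 0 |
| Postmenopausal, with tubal ligation | 0 | 0 | 0 | 0 |
| Premenopausal, tubal ligation only | 0 | 0 | 0 | 0 |

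**Step 2: does anything else restore a test in the last row?** Exclusion criterion 49 removes a woman with a positive screening test, but none is scheduled for her. The FSH test for women under 50 establishes menopause, not pregnancy. Section 8.2.11 allows extra safety samples if clinically indicated, which is discretionary. Section 8.2.11.2 asks women to report a suspected pregnancy, and Section 8.3.10.1 stops the product if one occurs. None of these is a scheduled test.

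**Step 3: size.** The Protocol gives no failure rate for tubal ligation. The only figure is the class bound in Appendix J, below 1% per year. It defines a category and is used here only as a ceiling.

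- Day 1 to last dose (Day 70): 0.01 × 70/365 = 0.0019, so below 0.19% per woman. Compounding gives the same: 1 − 0.99^(10/52) = 0.0019.
- Adding the roughly 3 weeks that Section 7.1.2 equates with 5 half-lives (to Day 91): 0.01 × 91/365 = 0.0025, so below 0.25%.
- These cover conception from Day 1. A pregnancy already present at screening is not counted.

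**Step 4: illustration for the trial.** The number of affected women is not stated. Assume, for scale only, 1% to 5% of 350.

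- Affected women: 0.01 × 350 = 3.5 to 0.05 × 350 = 17.5.
- Expected pregnancies from Day 1 to last dose: below 3.5 × 0.0019 = 0.007 to below 17.5 × 0.00192 = 0.034.
- On active product (4 of 5 arms): 0.8 × 0.0067 = 0.005 to 0.8 × 0.034 = 0.027.
- Added tests: 3.5 × 8 = 28 to 17.5 × 8 = 140.

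**The case against.** The strongest reply is that the rule is coherent. Criterion 6 and Appendix J agree that tubal ligation is sterilisation. Table J13 is written for partners of male participants, and a procedure can be both a sterilisation and an acceptable contraceptive method. Men are handled alike: the contraceptive duty falls on nonsterilised men, while a vasectomised partner also appears in Table J13. Surgical status must be documented, whereas menopause at 50 or over rests on history. Testing where status is less certain and waiving where surgery is proven is a defensible principle.

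Much of this stands. A reader might infer that the testing rules contradict one another. They do not: they apply one label consistently, and the conflict is only in how tubal closure is classed in the two roles. The documentation requirement is a real safeguard, but it shows that the operation was done and cannot detect a pregnancy. The parallel with men is also incomplete, since footnote b of Table J13 accepts vasectomy only with evidence that it worked.

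A reader might also take 1% per year as the failure rate of tubal occlusion. The documents do not support that: it is a ceiling for a class that also holds pills and abstinence, and a rate near zero would satisfy it. Nor should the bound be carried to Week 36 as exposure risk (0.01 × 252/365, below 0.69%), because most of the interval after Day 70 lies beyond the 5 half-lives in Section 7.1.2.

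**Conclusion.** The point holds as a small fetal-safety gap. A premenopausal woman whose only procedure is tubal ligation is eligible and has 0 of 8 scheduled tests. Appendix J itself classes tubal occlusion in a partner as contraception with a non-zero permitted failure rate.

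At the class bound, her chance of conceiving between Day 1 and the last dose is below about 0.19%. Under the assumed 1% to 5% prevalence, that is at most hundredths of an expected pregnancy in the trial, and one participant in five receives placebo. The conclusion rests on the text of the testing rules and not on that prevalence, which the Protocol does not give. That this is the admitted group in which a test is most likely to matter is a clinical judgement, not a statement in the Protocol.

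A reader might go further and ask that the waiver be withdrawn from every woman with tubal ligation. That is not supported: it would add 8 tests for each postmenopausal woman with the procedure without addressing this gap. No efficacy result, error rate or power figure is affected.

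**What to change.** Keep tubal ligation as an entry route. In the criterion 6 note, Table 1 footnote t, the Section 8 Day 1 list, and Sections 8.2.11, 8.2.11.2 and 8.3.10.1, extend the serum and urine tests to women who are not postmenopausal under criterion 6 and whose only sterilising procedure is bilateral tubal ligation.

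Leave the waiver as it is for hysterectomy, bilateral oophorectomy, and postmenopausal women with tubal ligation. Do not replace the Appendix J list with a cross-reference to criterion 6. Criterion 6 omits bilateral salpingectomy, so that edit would settle a separate mismatch without anyone having decided it.

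The cost is wording in the next amendment and at most 8 tests per affected woman, using tests and visits already in the schedule. There is no new visit and no change to eligibility.

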Appendix K Half-lives of Nonsteroidal Anti-inflammatory Drugs and Other Analgesics

Analgesic	Half-life (hours)	Minimum washout period
Azapropazone	15.0	4 days
Bromfenac	1.3-3.1	2 days
Capsaicin (cream, ointments, patches)	2.0	2 days
Carprofen	12.0	3 days
Celecoxib	11.0	3 days
Codeine	3.5	2 days
Diclofenac	1.1	2 days
Diclofenac gels	1.9	2 days
Diclofenac/misoprostol	2.4-9.0	2 days
Diflusinal	13.0	3 days
Dipyrone	2.0-5.0	2 days
Etodolac	6.0	2 days
Fenbufen	11.0	3 days
Fenoprofen	2.5	2 days
Flufenamic acid	1.4	2 days
Flurbiprofen	3.8	2 days
Ibuprofen	2.1	2 days
Indomethacin	4.6	2 days
Ketoprofen	1.8	2 days
Ketorolac	4.0-9.0	2 days
Lidocaine patch or EMLA (lidocaine/prilocaine)	2.0	2 days
Meclofenamate	2.0-4.0	2 days
Mefenamic acid	2.0	2 days
Meloxicam	16.0-20.0	5 days
Meperidine	3.7	2 days
Mexiletine	6.0-17.0	4 days
Nabumetone	26.0	6 days
Naproxen	14.0	3 days
Oxaprofen	40.0-50.0	11 days
Oxaprozin	58.0	13 days
Phenylbutazone	68.0	15 days
		-

Table K14Half-lives of NSAIDs and Other Analgesics

Table K14	Half-lives of NSAIDs and Other Analgesics
-----------	---

Analgesic	Half-life (hours) Minimum perio	
Piroxicam	57.0	12 days
Pirprofen	3.8	2 days
Salicylates	2.0-15.0	4 days
Sulindac	14.0	3 days
Suprofen	2.5	2 days
Tenoxicam	60.0	13 days
Tiaprofenic acid	3.0	2 days
Tolmetin	1.0	2 days
Tramadol	5.9	2 days

Appendix L Abbreviations

Abbreviation or special term	Explanation	
ABPM	ambulatory blood pressure monitoring	
АСРА	anti-citrullinated protein antibodies	
ADA	antidrug antibody	
AE(s)	adverse event(s)	
AESI	adverse event of special interest	
ALP	alkaline phosphatase	
ALT	alanine aminotransferase/transaminase	
ANCOVA	analysis of covariance	
anti-HBc	antibody to hepatitis B core antigen	
AST	aspartate aminotransferase/transaminase	
BOCF	baseline-observation-carried-forward	
BP	blood pressure	
Caverage	average observed drug concentration over the dosing interval	
CFR	Code of Federal Regulations	
C _{max}	maximum (peak) observed drug concentration	
COVID-19	Coronavirus disease 2019	
COX-2	cyclooxygenase-2	
CRP	C-reactive protein	
CSP	clinical study protocol	
CSR	clinical study report	
CCI		
DILI	drug induced liver injury	
DMARD(s)	disease-modifying antirheumatic drugs	
DSIS	Daily Sleep Interference Scale	
DSMB	Data and Safety Monitoring Board	
DNA	deoxyribonucleic acid	
ECG	electrocardiogram	
eCOA	electronic clinical outcomes assessment	
eCRF	electronic case report form	
ED ₅₀	half of the E _{max}	
EDC	electronic data capture	
E _{max}	maximum response	
EOT	end-of-treatment	
ePRO	electronic patient-reported outcome	

Abbreviation or special term	Explanation	
ET	early termination	
FDA	United States Food and Drug Administration	
FSH	follicle-stimulating hormone	
FTIH	first-time-in-human	
FU	follow-up (as adjective)	
GCP	Good Clinical Practice	
HBsAg	hepatitis B surface antigen	
HBV	hepatitis B virus	
НСР	health care provider	
CCI		
HCV	hepatitis C virus	
HIPAA	Health Insurance Portability and Accountability Act	
HIV	human immunodeficiency virus	
HL	Hy's Law	
IB	Investigator's Brochure	
IATA	International Airline Transportation Associations	
ICF	informed consent form	
ICH	International Council for Harmonisation	
IEC	Independent Ethics Committee	
IgE	immunoglobulin E	
INR	international normalised ratio	
IP	investigational product	
IRB	Institutional Review Board	
IRT	Interactive Response Technology	
IV	intravenous	
KL	Kellgren and Lawrence	
LOCF	last-observation-carried-forward	
LVEF	left ventricular ejection fraction	
MAD	multiple-ascending dose	
MCP-Mod	multiple comparison procedure-modelling	
CCI		
MRI	magnetic resonance imaging	
CCI		
NGF	nerve growth factor	
NRS	numerical rating scale	

Abbreviation or special term	Explanation	
NSAIDs	nonsteroidal anti-inflammatory drugs	
OA	osteoarthritis	
OMERACT-OARSI	Outcome Measures in Rheumatology-Osteoarthritis Research Society International	
OTC	over the counter	
PD	pharmacodynamics	
PDN	painful diabetic neuropathy	
PEF	peak expiratory flow	
PGA	Patient's Global Assessment	
PHL	Potential Hy's Law	
РК	pharmacokinetic(s)	
Q2W	every 2 weeks	
QTcF	corrected QT interval by Fredericia	
RA	rheumatoid arthritis	
RBC(s)	red blood cell(s)	
RNA	ribonucleic acid	
RPOA	rapidly progressive osteoarthritis	
RPOA-1/RPOA-2	rapidly progressive osteoarthritis type 1/ rapidly progressive osteoarthritis type 2	
RPOA-AC	Rapidly Progressive Osteoarthritis Adjudication Committee	
RTSM	Randomisation and Trial Supply Management	
SAD	single-ascending dose	
SAE(s)	serious adverse event(s)	
SAP	statistical analysis plan	
SARS-CoV-2	severe acute respiratory syndrome coronavirus 2	
SAS	Survey of Autonomic Symptoms	
С		
CF scFv	single chain variable domain fragment	
SD	standard deviation	
CCI		
SIF	subchondral insufficiency fracture	
SoA	schedule of assessments	
SUD	substance use disorders	
SUSAR	serious adverse reactions	
TB	tuberculosis	
TBL	total bilirubin	
TEAE	treatment-emergent adverse event	

Abbreviation or special term	Explanation	
TNF	tumour necrosis factor	
ΤΝFα	tumour necrosis factor-alpha	
TNFR2	TNF receptor 2	
TNSn	Total Neuropathy Score-nurse	
TPV	third-party vendor	
ULN	upper limit of normal	
WFI	water for injection	
WOMAC	Western Ontario and McMaster Universities Osteoarthritis	
CCI		

